8.2 Secondary Objective Outcome Measures: Acute Care Utilization

The secondary endpoint is a count measure of the number of days of acute care utilization in the 2 years after randomization. This measure includes visits to urgent care clinics or emergency departments (EDs), as well as days hospitalized. As above, acute care utilization will be determined from EHR and insurance claims data when available (Table 6). Each day with a visit to an urgent care or ED will be counted as 1 day (even if the patient stays overnight). For hospitalizations, the number of days will be the number of days from admission to discharge, inclusive. If a patient is admitted from urgent care or an ED, the ED or urgent care day is not (double) counted. Final definitions and algorithms used to define this outcome will be provided in the SAP.

Table 7. Additional Outcomes: Assessed in the 2 Years After Randomization.

Additional Implementation Outcomes	
Newly recognized OUDs (Reach)	Number of patients* with a new ICD code for OUD during follow-up who did not have an OUD diagnosis in the three years prior to randomization
Initiation of OUD treatment (Reach)	Number of patients* who initiate buprenorphine or injectable naltrexone with an OUD diagnosis (> 28 days) during follow-up: any initiation and separately for initiation of each type of medication.
Retention in OUD treatment (Implementation effectiveness)	Number of patients* initiating OUD treatment during follow-up who receive OUD treatment on 80% of days available after initiation and median days of OUD treatment after initiation for patients with at least 6 and 12 months available for follow-up. (Patients not retained in treatment per the EHR are considered no longer in treatment, an added secondary outcome).
Contiguous days in treatment (Implementation effectiveness)	Days of OUD medication treatment with no gap in orders or refills exceeding 60 days ⁷³ will be used to assess retention as well
Cross-over between clinic arms	The number of patients with OUDs assigned to each clinic (PROUD and UPC) in the 3 years prior to randomization who are seen in the other clinic post randomization,
Cross-over between systems (patients with OUD WA only)	The proportion of patients treated for OUDs in each clinic who have insurance from another health system (i.e., patients seen at Multicare who have KP insurance and patients seen in KP Washington who have outside insurance).

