#### 3.3 Objective 2 Primary Study Sample ("Pre-randomization Sample")

The primary effectiveness (Objective 2) outcome, along with secondary effectiveness measures, will be analyzed in the subset of patients from the full sample of eligible patients who had (1) an eligible PC visit at a PROUD trial PC clinic during the pre-randomization period, (2) a documented OUD diagnosis during the pre-randomization period, and (3) who were age  $\geq 16$  as of the start of the baseline period (two years pre-randomization). This latter criterion ensures that the patient has at least 2 years pre-randomization in which to have an eligible PC visit (in which they are  $\geq 16$  years of age). Clinic assignment for the Objective 2 primary sample will be the same as above. Because study sample is defined using pre-randomization data, this sample is also referred to as the Objective 2 pre-randomization sample.

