    - ii. Drop naltrexone injections in the post randomization period if there are not 2+ visits with an OUD/OD diagnoses (can be 1 OUD and 1 OD code) in the pre or post randomization period.
- 7) In the pre and post-randomization periods, create continuous use episodes defined as OUD treatments with gaps  $\leq 7$  days between the runout of one order/procedure and the start date of the subsequent (other cut points to be evaluated in sensitivity analyses after summarizing the distribution of gaps). For example, two OUD treatment episodes with treatment episode 1 start 1/1/2018 and runout 1/15/2018 and treatment episode 2 starting 1/17/2018 and runout 2/5/2018 are rolled into one episode of continuous treatment (start

1/1/2018 and end 2/5/2018). In general, this gap applies to same medication orders/procedures and different medications.

- a. One exception is that gaps of  $\leq 14$  days between the runout of a buprenorphine order and subsequent naltrexone XR injections are allowed in defining continuous use episodes to account for required washout periods prior to naltrexone XR injection.
- 8) Pre and post randomization episodes are not allowed to overlap. They will be left and right censored accordingly. For example, a treatment episode of 90 days with 15 days in the post randomization period (includes randomization date) will be split into two episodes with one episode contributing 75 days of treatment pre-randomization and a second episode contributing 15 days of treatment post randomization.
- 9) Add the number of days of each continuous use episode to arrive at total days of OUD treatment in the distinct periods of pre-randomization and post-randomization. The algorithm does not allow for double counting of any overlapping orders or procedures.

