### 4.3 Definitions of Secondary Measures

Additional secondary measures will be analyzed to describe outcome measures reflecting processes of care, implementation, and effectiveness. The following table describes each of the measures that will be examined either descriptively, or through formal modeling, as described in the statistical analysis section below. Measures will be calculated broadly in the full study sample to facilitate analyses across different study samples. For example, we will calculate the number of days of OUD medication treatment for each patient, which will be summed across patients as part of the primary Objective 1 outcome and will also be analyzed at a patient-level among patients with an OUD diagnosis pre-randomization. Other implementation measures (e.g., number of patients treated) will be analyzed in both the full study sample of all patients with a visit, as well as in the subsample of these patients who had an OUD diagnosis pre-randomization.

**Table 2: Primary, Secondary, and Other Outcomes Measured During Post-Randomization Period Based on EHR Data (\*measures from clinicaltrials.gov)**

Outcome Measures

*Objective 1. Patient-days of OUD medication treatment (primary outcome). Clinic-level number of patient-days of OUD treatment with buprenorphine and XR-NTX documented in the EHR during the period from randomization until two years after, reported per 10,000 PC patients in the clinic in the two years post-randomization.

*Objective 2. Acute care utilization (secondary outcome). Patient-level number of days of acute care utilization during the period from randomization until two years after, among patients with an OUD diagnosis documented in the EHR in the three years prior to randomization.

Other Outcome Measures of Implementation

*Newly diagnosed OUD (Implementation Reach). Clinic-level number of patients with a new International Classification of Disease (ICD) code for OUD documented in the EHR during the period from randomization until two years after who did not have an OUD diagnosis documented in the EHR in the three years prior to randomization, reported per 10,000 patients in the PC clinic in the two years post-randomization.
 
This measure will also be estimated for any OUD diagnosis (new and previous diagnoses).

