f Prescribers determined from medication orders in the electronic health records. Providers assigned to clinics based on number of visits with patients in the clinic post-randomization.

Abbreviations: NCM – nurse care manager; ITT- intent to treat; OUD: opioid use disorder; SD – standard deviation; XR-NTX – extended release injectable naltrexone

Supplemental Table 1a is the main Table 1a above by health system
Supplemental Table 1b is the main Table 1b above by health system
Supplemental Table 2 is the main Table 1a above but using data for the post randomization period and among patients with an eligible visit post randomization (closest to study end as anchor for variables)
Supplemental Table 3 is the main Table 2 above by health system

Supplemental Table 4 is the main Table 2 above with OUD treatment related outcomes stratified by newly initiated treatmenta versus on-going treatmentb, and the OUD diagnosis outcome stratified by newly diagnosed OUDc versus prevalent OUDd.
 
a OUD treatment in the 2 years post randomization and no OUD treatment in the prior 365 days
 
b OUD treatment post-randomization that does not meet criteria for initiated above
 
c 1+ OUD diagnosis anywhere in the health system in the 2 years post randomization and no OUD diagnosis in the 2 years pre randomization.
 
d 1+ OUD diagnoses in both the 2 years pre randomization and 2-years post randomization

Supplementary Table 5. Sensitivity analyses focused on assumptions made in estimating patient-years of OUD medication treatment, clinic-level results in the 2 years post randomization			
	Patient years treatment /10,000 patients seen in clinic post-randomizationa		Mean difference (95% CI)b
	6 intervention clinics	6 usual care clinics	
Primary outcome			---
Limited to the time period in which the NCM started seeing patients d			
Limited to health systems that successfully implement the MA model e			
Covariate adjusted c			
Using a combination of medication orders and pharmacy dispensings			
Adding Methadone Maintenance Therapy data from 1-2 sites, per 10,000 patients seen in the 1-2 clinics post randomization			
Adding pharmacy dispensings and MMT data at the 1-2 sites with these sources of data			

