**Table 2.** Effect of PROUD Intervention on OUD treatment among patients with documented OUD pre-randomization

Measure of OUD treatment in 2 years post-randomization	Intervention (n=xxx)	Usual Care (n=xxx)	Treatment effect a		P value
Main treatment measure: days of OUD treatment c	mean (IQR) days per year b		RR	95% CI	
Primary sample with OUD pre-randomization (intention to treat)					
Sub-samples and/or follow-up periods restricted to:					
a. Clinics that successfully implemented MA model d					
b. Time period in which the NCM was seeing patients					
c. Patients with PC visit to assigned clinic post-randomization					
d. Both b and c					
Secondary treatment measures	N (%) b		OR	95% CI	
OUD treatment duration					
0 days					
1-30 days					
31-90 days					
91-180 days					
180+ days (sustained OUD treatment)					
Initiation of new episode of OUD treatment e					
Initiated and 80% adherence to treatment					
Initiated and sustained OUD treatment					

a Estimated from a mixed-effect model with clinic-specific random intercept, adjusted for days of OUD treatment during the baseline period

b Unadjusted estimates. We note that if we observe a statistically significant difference from the adjusted model, but the unadjusted estimates appear similar then we plan to also calculate the adjusted estimates

c OUD treatment defined as having a medication order or procedure code for buprenorphine formulations that are indicated for OUD or having a medication order or procedure code for XR-NTX and 2+ visits with diagnosis code for OUD or opioid overdose during the pre-randomization period.

d Successful implementation is defined as the NCM at the intervention clinic at that HCS seeing at least 30 patients. We note that estimates from the secondary analyses of the main treatment measure may instead be separated into a different paper or included in a supplemental table.

e OUD treatment following a period of 365 days with no OUD treatment

**Table 3.** Effect of PROUD Intervention on acute care utilization among primary care patients with documented OUD pre-randomization

Measure of Acute Care Utilization in 2 years post-randomization	Intervention	Usual Care	Treatment	95% CI	P value
	(n=xxx)	(n=xxx)	Effect a		
	mean (IQR) days per year b		RR		

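### Newly diagnosed OUD is defined with a 3-year look-back, but the only results shell that reports it uses 2 years, so patients last coded in year -3 are shown as new

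*SAP*

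**What the plan says.** **Definition.** SAP Table 2 (Section 4.3) lists "Newly diagnosed OUD (Implementation Reach") with an asterisk, which the table title explains as "measures from clinicaltrials.gov". It is the clinic-level number of patients with a new OUD code in follow-up "who did not have an OUD diagnosis documented in the EHR in the three years prior to randomization", per 10,000 patients. Protocol Table 7 (Section 8.2) has the same look-back: "who did not have an OUD diagnosis in the three years prior to randomization".

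**Reporting.** In SAP 10.1, the Table 2 shell of the Objective 1 paper has a row for any OUD diagnosis after randomization and none for new diagnoses. Supplemental Table 3 repeats that shell by health system. Supplemental Table 4 is the only shell that splits out new diagnoses. Its footnote c reads: "1+ OUD diagnosis anywhere in the health system in the 2 years post randomization and no OUD diagnosis in the 2 years pre randomization". Footnote d calls OUD prevalent when there is a code both in the 2 years before and in the 2 years after randomization.

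**Periods.** SAP 2.3 sets the pre-randomization period at 3 years (2.8 at one health system, treated as 3 throughout). SAP 2.3.1 defines a separate 2-year baseline period, described for covariates. SAP 2.6 has data collected from 3 years before randomization.

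**The concern.** The shell that will produce the result does not apply the outcome's own rule. If it is programmed as written, a patient with OUD already on record in year -3 can be reported as a new recognition of OUD.

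New diagnosis is one of the trial's Reach measures. SAP 4.1 says PROUD clinic providers are likely to document OUD because the nurse manual leads them to, and Protocol 11.2.2 expects the intervention to increase diagnosis. Coding again a patient last coded in year -3 is therefore plausibly more frequent in the PROUD arm, and the 2-year rule would count that re-documentation as a new case. The registered measure would then have no results row under its registered definition, and programmers would have to choose between two windows.

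**Working it through.** No sample size, power or error-rate figure is involved, so there is no plan figure to reproduce. The check is a comparison of two rules.

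**Inputs.** Definition: no code in years -3, -2 or -1 (SAP Table 2). Shell: no code in years -2 or -1 (Supplemental Table 4, footnote c). Both require a post-randomization code.

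| Coded in year -3 | Year -2 | Year -1 | SAP Table 2 | Supplemental Table 4 |
|---|---|---|---|---|
| no | no | no | new | new |
| no | no | yes | not new | not new |
| no | yes | no | not new | not new |
| no | yes | yes | not new | not new |
| **yes** | **no** | **no** | **not new** | **new** |
| yes | no | yes | not new | not new |
| yes | yes | no | not new | not new |
| yes | yes | yes | not new | not new |

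One pattern of eight differs. At the system with 2.8 years of data, year -3 means the 0.8 years from -2.8 to -2.0. Footnotes c and d together cover everyone with a follow-up code, so the discordant patients are not dropped; they land in the new category. With the full pre-randomization period in both footnotes, all eight patterns agree.

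**Consistency with the same paper.** Supplementary Table 5 has rows for patients with and without OUD before randomization, following SAP 5.2.5. With the pre-randomization period at 3 years, a clinic patient coded only in year -3 is a known case there, but new in Supplemental Table 4.

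**Size, for illustration only.** The Phase 1 counts in SAP 6.2.1 sum to 9 + 12 + 63 + 39 + 58 + 200 + 100 + 49 + 27 + 10 + 388 + 290 = 1,245 patients with an OUD diagnosis over 3 years. Let p be the share coded in the earliest year only and q the share of those coded again in follow-up. Neither is in the documents. Discordant patients = 1,245 × p × q:

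- p = 5%, q = 25%: 15.6, or 1.3 per clinic
- p = 10%, q = 50%: 62.2, or 5.2 per clinic
- p = 30%, q = 75%: 280.1, or 23.3 per clinic

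These cannot be put on the outcome's per-10,000 scale, because the post-randomization denominators are not given. No arm difference is computed, because the documents support its direction but give no re-coding rate by arm.

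**Related wording on XR-naltrexone.** For post-randomization injections, SAP 4.1.1 step 6c wants two or more OUD or overdose visits, which "can be 1 OUD and 1 OD code) in the pre or post randomization period"; Appendix A agrees. The Objective 1 shells (Table 2, Supplementary Table 5, Table 7) limit the codes to 2 years before or 2 years after randomization. The Objective 2 Table 2 shell, which reports post-randomization treatment, asks for "2+ visits with diagnosis code for OUD or opioid overdose during the pre-randomization period". That matches the footnote to baseline Table 1b, where it fits, and looks carried over.

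**The case against.** The strongest reply is that the SAP body governs. Section 5.6 analyses the secondary clinic-level outcomes as listed in SAP Table 2, which means 3 years; the 2-year text is only a footnote to a supplemental stratification. That settles which definition should prevail, but it does not correct the shell, and no other shell carries the outcome.

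The 2-year baseline period might be offered as the reason. SAP 2.3.1 justifies it for covariates, on the ground that all clinics have those data. It does not mention the outcome look-back, and even the shortest system has 2.8 years.

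It is also fair that this is a secondary outcome with no multiplicity control, to be interpreted cautiously (Protocol 11.5). That limits the weight of the point.

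Three stronger readings are tempting and not supported:

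- *Everyone coded in year -3 becomes new.* Only those with no code in years -2 and -1, and a further code in follow-up, are affected.
- *The two trial papers classify the same patients in opposite ways.* The Objective 2 primary sample does require "a documented OUD diagnosis during the pre-randomization period", but also a trial-clinic visit in that period and age 16 or over at the start of baseline. Footnote c counts diagnoses anywhere in the health system, and Objective 2's post-randomization group can include patients with earlier OUD elsewhere in the system. Only some discordant patients would carry opposite labels.
- *Objective 2 patients lose their XR-naltrexone days.* SAP 4.3 describes treatment days calculated for each patient and used in both objectives, and 4.1.1 and Appendix A give the pre-or-post rule for them. A footnote slip is the likelier explanation.

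**Conclusion.** The conflict is real and narrow. SAP Table 2 and Protocol Table 7 require 3 clear years; Supplemental Table 4 requires 2, without a stated reason. Following the shell would report as new those patients whose only pre-randomization code is in year -3 and who are coded again.

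The likely direction, if re-coding differs by arm as the SAP's own expectation suggests, favours the intervention on this outcome. The size is unknown: the range of about 16 to 280 patients rests on two assumed percentages applied to Phase 1 counts, and a reader should not infer any number for an arm imbalance from it. The look-back does not touch the primary outcome or the Objective 2 acute-care result. It should be corrected because this is a registered outcome and the shell is its only planned display. The XR-naltrexone footnotes are a separate, minor wording matter and add no weight to this conclusion.

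**What to change.** In Supplemental Table 4, change footnote c to no OUD diagnosis in the pre-randomization period (3 years; 2.8 at one health system) with at least one in follow-up, and footnote d to a diagnosis in both that period and follow-up. If the 2-year look-back is of interest, add it as a labelled sensitivity row.

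The cost is two footnotes and one date limit in the code; the data are already extracted. The shorter window at one system remains, but the SAP already treats it as 3 years.

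Separately, align the XR-naltrexone footnotes in the Objective 1 shells (Table 2, Supplementary Table 5, Table 7) and footnote c of the Objective 2 Table 2 shell with the pre-or-post rule in 4.1.1 and Appendix A. Step 6a of 4.1.1 also tabulates diagnoses over 2 pre-randomization years for adjudication; state whether that is deliberate.

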**Retention measures of OUD treatment (Implementation Fidelity).**

**\*Retention in OUD treatment.** Clinic-level number of patients initiating§ OUD treatment during the period from randomization until two years after randomization as documented in the EHR, who also receive OUD treatment on 80% of days available after initiation, reported per 10,000 PC patients in the clinic in the two years post-randomization.

**Retention in OUD treatment for  $\geq 6$ -months** Clinic-level number of patients initiating§ OUD treatment during the period from randomization until two years after randomization as documented in the EHR, who remain on treatment for  $\geq 6$  months after initiation, reported per 10,000 PC patients in the clinic in the two years post-randomization.\*\*\*

**Discontinuation of OUD treatment.** Clinic-level number of patients initiating§ OUD treatment during the period from randomization until two years after randomization as documented in the EHR, who discontinue treatment (defined as a gap of 60+ days), reported per 10,000 PC patients in the clinic in the two years post-randomization.

§See definition of initiation above;

\*\*\*Excludes patients whose only eligible PC visit occurred in the last 6 months of the post-randomization period or who began OUD treatment in the last 6-months of the post-randomization period. Measures of retention above will also be estimated for all subjects regardless of new or on-going treatment and for subjects with on-going treatment.

**Number of buprenorphine prescribers (Implementation Fidelity).** Clinic-level number of buprenorphine prescribers† during the period from randomization until two years after randomization as documented in the EHR, who prescribe buprenorphine, reported per 10,000 PC patients in the clinic in the two years post-randomization.

Number of buprenorphine prescribers will also be reported per X total prescribers in the clinic in the two years post-randomization.

†Prescribers determined from medication orders in the electronic health records. Providers assigned to clinics based on number of visits with patients in the clinic pre-randomization.

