a Defined as having a medication order or procedure code for buprenorphine formulations that are indicated for OUD or having a medication order or procedure code for XR-NTX and 2+ visits with diagnosis code for OUD or opioid overdose during the pre-randomization period. b Restricted to subjects who entered the sample (i.e., had a PC visit) in the 6 months-2.0 years prior to randomization to allow for at least 6 months of follow-up c Defined as a gap in OUD treatment of 60 days d at any time during pre-randomization treatment Abbreviations: OUD – opioid use disorder; SD – standard deviation; XR-NTX – extended release injectable naltrexone		

**Table 2.** Clinic level primary and secondary implementation outcomes of the Primary Care Opioid Use Disorders Treatment (PROUD) trial, during 2 years post randomization.

Implementation measures	6 intervention clinics	6 usual care clinics	P value a
	Mean (SD) across clinics per 10,000 patients seen in clinic post randomization		
Patient years of OUD treatment (primary outcome b )			
Proportion of clinics' patient population post-randomization with:			
Any OUD diagnosis post-randomization			
Any OUD treatment b			
80% of days covered by OUD treatment			
≥ 6-months retention in OUD treatment b,c			
Discontinuation of OUD treatment b,d			
Buprenorphine daily dose ≥16 mg e			
Naloxone prescribed			
Number of buprenorphine prescribers f			

a Random effects model adjusted for the outcome measure at baseline (two years prior to randomization)

b Treatment defined as having a medication order or procedure code for buprenorphine formulations that are indicated for OUD or having a medication order or procedure code for XR-NTX and 2+ visits with diagnosis code for OUD or opioid overdose (diagnosis codes can be during the 2-years pre or 2-years post randomization).

c Restricted to subjects who entered the sample (i.e., had a PC visit) in the 1 day to 1.5 years post randomization (1 day to 12 months for the site randomizing 6-months late) to enable at least 6 months of follow-up

d Discontinuation defined as a gap in OUD treatment of 60 days

e At any time during OUD treatment post randomization

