**Table 7.** Clinic level primary and secondary implementation outcomes of the Primary Care Opioid Use Disorders Treatment (PROUD) trial among patients receiving OUD treatment during the 2 years post randomization.

Randomization:			
Scaled implementation measure among treated patients	6 intervention clinics	6 usual care clinics	P value a
	Mean (SD) across clinics per 100 patients treated in the clinic post randomization		
Patient years of OUD treatment b			
Primary outcome (ITT analysis) c			
Limited to the time period after the NCM started seeing patients d			
Limited to health systems that successfully implement the MA model e			
Number of patients with:			
Newly initiated treatment a, f			
On-going treatment a,g			
80% of days covered by OUD treatment			
Newly initiated treatment a, f			
On-going treatment a,g			
≥ 6-months retention in OUD treatment h			
Newly initiated treatment a,f			
On-going treatment a,g			
Discontinuation of OUD treatment i			
Newly initiated treatment a,f			
On-going treatment a,g			
Buprenorphine average daily dose in mg			
Buprenorphine daily dose ≥16 mg j			
Naloxone prescription			

a Random effects model adjusted for the primary outcome measure at baseline (two years prior to randomization)

b Defined as having a medication order or procedure code for buprenorphine formulations that are indicated for OUD or having a medication order or procedure code for XR-NTX and 2+ visits with diagnosis code for OUD or opioid overdose (diagnosis codes can be during the 2-years pre or 2-years post randomization)

c Includes all clinics and all follow-up time post randomization

d Time period during which NCM seeing patients: X days for clinic A, X days for clinic B, X days for clinic C, X days for clinic D, X days for clinic E, and X days for clinic F

e Successful implementation defined as the nurse care manager seeing at least 30 patients. Analysis includes X of 6 health systems.

f OUD treatment in the 2 years post randomization and no OUD treatment in the prior 365 days

g OUD treatment in post-randomization, but not meeting criteria for initiated

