h Restricted to subjects who entered the sample (i.e., had a PC visit) in the 1 day to 1.5 years post randomization (1 day to 12 months for the site randomizing 6-months late) to enable at least 6 months of follow-up

[figure not shown]
i defined as a gap in OUD treatment of 60 days

j 16 mg or more of buprenorphine/day at any time post randomization

[figure not shown]
Abbreviations: NCM – nurse care manager; ITT- intent to treat; OUD: opioid use disorder; SD – standard deviation; XR-NTX – extended release injectable naltrexone

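### Three SAP shell footnotes omit the treatment-start exclusion that SAP 4.3 sets for 6-month retention; in Objective 1 Table 7 this understates retention among new starters

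*SAP*

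**What the plan says.** SAP Section 4.3 (Table 2, retention measures) counts initiators who stay on treatment for at least 6 "months after initiation, reported per 10,000 PC patients in the clinic in the two years post-randomization". The note attached to the measure has two limbs. The first: "Excludes patients whose only eligible PC visit occurred in the last 6 months of the post-randomization period". The second: "or who began OUD treatment in the last 6-months of the post-randomization period".

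The Objective 1 shells in SAP Section 10.1 restrict the same measure differently:

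- **Table 1b, footnote b (baseline):** "Restricted to subjects who entered the sample (i.e., had a PC visit) in the 6 months-2.0 years prior to randomization".
- **Table 2, footnote c, and Table 7, footnote h:** "Restricted to subjects who entered the sample (i.e., had a PC visit) in the 1 day to 1.5 years post randomization", with 12 months in place of 1.5 years at the health care system (HCS) that randomized late. The stated purpose is "to enable at least 6 months of follow-up".

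None of the three mentions when treatment started. The column header of Table 7 is "Mean (SD) across clinics per 100 patients treated in the clinic post randomization". Its footnote f defines newly initiated treatment as "OUD treatment in the 2 years post randomization and no OUD treatment in the prior 365 days", with no cut-off for late starts. SAP Section 5.6 points to Table 2 of Section 4.3 for the secondary outcomes, but does not say that a differing shell footnote gives way to it.

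**The concern.** The footnotes secure 6 months from a PC visit. Retention needs 6 months from the start of treatment. SAP Appendix A (the treatment-day step) truncates treatment days at the end of the period, so a patient seen in month 3 whose first order is in month 21 has at most 3 months of countable treatment. SAP 4.3 removes that patient. The footnotes do not.

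Where the denominator is all clinic patients this hardly matters. Table 7 has treated patients as its denominator, separates new from ongoing treatment and carries a P value column. There, a patient who stays in without being able to qualify pulls the retention figure down. The share of such patients need not be equal in the two arms. Two analysts working from the same SAP could report different retention figures.

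**Working it through.** The plan gives no figure to reproduce. The check compares the two rules and then asks how much the difference could matter.

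**1. Windows.** Follow-up is 24 months in five HCSs and 18 months in the sixth (SAP 2.4). Subtracting 6 gives 24 − 6 = 18 months and 18 − 6 = 12 months. These match the footnotes, so the cut-offs are right; they are applied to the visit and not to the treatment start.

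**2. Who is treated differently.** Only late starters (first order in the last 6 months) who also had a PC visit between day 1 and month 18 (month 12 at the late HCS). Late starters without such a visit are already removed by footnotes c and h.

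**3. Per-10,000 scale (Table 2).** Assume 10,000 patients seen, 100 starters, 25 of them late, and 60% retention among the other 75.

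- Retained: 75 × 0.60 = 45.
- Shell rule: 45 / 10,000 = 45.0 per 10,000.
- Late starters also removed from the denominator: 45 / 9,975 = 45.1 per 10,000.

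Late starters are in the numerator under neither rule. Table 1b uses the same kind of scale.

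**4. Per-treated scale (Table 7).** Let R be true 6-month retention, L the share of starts that are late, and q the share of late starters who pass the visit filter. If the newly initiated row is scaled by initiators and footnote h filters the denominator:

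reported retention = R × (1 − L) / [(1 − L) + qL]

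L, q and R are assumptions; the documents give no distribution of start dates. With uniform starts, L = 6/24 = 25%, or 6/18 = 33% at the late HCS. Protocol 7.1.1 plans 6 months of start-up and then 18 months of inductions in intervention clinics. If no starts occurred before that, L would be 6/18 = 33%, or 6/12 = 50% at the late HCS. For R = 60%:

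| L | q = 0 | q = 0.23 | q = 0.5 | q = 1 |
|---|---|---|---|---|
| 25% | 60.0% | 55.7% | 51.4% | 45.0% |
| 33% | 60.0% | 53.8% | 48.0% | 40.0% |
| 50% | 60.0% | 48.8% | 40.0% | 30.0% |

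With the SAP 4.3 start rule applied to this denominator, every cell is 60%.

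**5. Between arms.** Take R = 70% in both arms, L = 25% in usual care and 33% in intervention clinics.

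- Usual care, q = 0.8: 0.70 × 0.75 / (0.75 + 0.20) = 55%.
- Intervention, q = 0.8: 0.70 × 0.667 / (0.667 + 0.267) = 50%, about 5 points lower.
- Intervention, q = 0.23: 0.70 × 0.667 / (0.667 + 0.077) = 63%, about 7.5 points higher.

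The sign depends on q. The value 0.23 is 1 − 0.77, from the Massachusetts figure in SAP 5.5.1 for patients new to the clinic. That is not the same quantity as q and serves only to mark out a range.

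**The case against.** The correct rule is already in the SAP. Section 4.3 defines the measure, Section 5.6 refers to it, and a footnote that restates one limb does not expressly revoke the other. That is fair, and it makes this an alignment error and not a missing definition. It does not dispose of the point: the footnotes give an explicit criterion of their own, repeat it in three tables, and add a cut-off for the late HCS that Section 4.3 does not state. A programmer filling Table 7 could reasonably code the footnote as it stands.

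The denominator is also uncertain. Read literally, the Table 7 header scales the newly initiated row by all treated patients, new and ongoing. On that reading the row is not a retention proportion among initiators, and the formula in the working does not apply. This stands, and is a reason to state the denominator.

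A reader might go further and infer that the retention results as a whole are biased, that the trial's retention hypothesis is undermined, or that a spurious arm difference of a given size will appear. The documents support none of these:

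- Tables 1b and 2 are essentially unaffected.
- The hypothesis in Protocol 3.2.3.1 concerns 12 months, not 6.
- The registered retention measure (treatment on 80% of days available after initiation) counts only days after the start, so late starters are not automatic failures there.
- The arm differences above change sign with an assumed input.

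SAP 5.2.6 advises caution about analyses among treated patients, but because the intervention can change who is in the denominator; it does not cover truncated follow-up.

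**Conclusion.** The inconsistency holds on the text alone: SAP 4.3 has a treatment-start exclusion that footnotes b, c and h lack, and footnotes c and h do not secure 6 months of follow-up after treatment starts. The consequence is confined to the 6-month row for newly initiated treatment in Table 7. Followed as written, that row is understated whenever some late starters had an earlier post-randomization PC visit, and possibly by different amounts in the two arms. Neither the size nor the direction of an arm difference can be fixed from the documents; the percentages in the working are illustrative and rest on assumed retention, start dates and visit patterns, and on an initiators-only denominator that the shell does not state. This is a secondary measure, and the primary outcome is unaffected. It is worth correcting before Table 7 is programmed.

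**What to change.** Carry both SAP 4.3 exclusions, visit and treatment start, into footnotes c (Table 2) and h (Table 7), with the cut-off at month 18, or month 12 at the late-randomized HCS. Put the matching rule for the pre-randomization period into footnote b (Table 1b). For Table 7, state that the exclusions apply to numerator and denominator alike, and that the newly initiated 6-month row is scaled by eligible initiators and not by all treated patients.

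The cost is footnote wording and one filter in the code. Fewer treated patients will enter the 6-month rows, so those estimates will be somewhat less precise.
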